## 7.2.4 Serious Adverse Events and Events of Clinical Interest

### 7.2.4.1 Serious Adverse Event

An AE or suspected adverse reaction is considered “serious” if, in the view of either the investigator or Merck, it results in any of the following outcomes:

- Death
- A life-threatening adverse drug experience – any adverse experience that places the patient, in the view of the initial reporter, at immediate risk of death from the adverse experience as it occurred. It does not include an adverse experience that, had it occurred in a more severe form, might have caused death.
- Inpatient hospitalization or prolongation of existing hospitalization
- A persistent or significant incapacity or substantial disruption of the ability to conduct normal life functions.
- A congenital anomaly/birth defect.

Important medical events that may not result in death, be life-threatening, or require hospitalization may be considered a serious adverse drug experience when, based upon appropriate medical judgment, they may jeopardize the patient or subject and may require medical or surgical intervention to prevent one of the outcomes listed in this definition. Examples of such medical events include allergic bronchospasm requiring intensive treatment in an emergency room or at home, blood dyscrasias or convulsions that do not result in inpatient hospitalization, or the development of drug dependency or drug abuse (21 CFR 312.32).

- Important medical events as defined above, may also be considered SAEs. Any important medical event can and should be reported as an SAE if deemed appropriate by the Principal Investigator or the IND Sponsor, IND Office.
- All events occurring during the conduct of a protocol and meeting the definition of a SAE must be reported to the IRB in accordance with the timeframes and procedures outlined in “The University of Texas M. D. Anderson Cancer Center Institutional Review Board Policy for Investigators on Reporting Serious Unanticipated Adverse Events for Drugs and Devices”. Unless stated otherwise in the protocol, all SAEs, expected or unexpected, must be reported to the IND Office, regardless of attribution (within 5 working days of knowledge of the event).
- **All life-threatening or fatal events**, that are unexpected, and related to the study drug, must have a written report submitted within **24 hours** (next working day) of knowledge of the event to the Safety Project Manager in the IND Office.
- Unless otherwise noted, the electronic SAE application (eSAE) will be utilized for safety reporting to the IND Office and MDACC IRB.

# Proprietary Information of MD Anderson

Protocol # 2016-0251

Date: February 24, 2020

108

- Serious AEs will be captured from the time of the first protocol-specific intervention, until 90 days after the last dose of drug, unless the subject withdraws consent or starts a new anti-cancer medication. Serious AEs must be followed until clinical recovery is complete and laboratory tests have returned to baseline, progression of the event has stabilized, or there has been acceptable resolution of the event.
- Additionally, any SAEs that occur after the 90 day time period that are related to the study treatment must be reported to the IND Office. This may include the development of a secondary malignancy.

Reporting to FDA:

- Serious AEs will be forwarded to FDA by the IND Sponsor (Safety Project Manager IND Office) according to 21 CFR 312.32.

It is the responsibility of the Investigator and the research team to ensure SAEs are reported according to the Code of Federal Regulations, GCPs, the protocol guidelines, Merck's guidelines, and IRB policy.

## 7.2.4.2 Events of Clinical Interest

Selected non-serious and SAEs are also known as ECIs and must be reported to Merck Global Safety and the M.D. Anderson IND office.

For the time period beginning when the ICF is signed until treatment allocation, any ECI, or follow up to an ECI, that occurs to any subject must be reported within 2 working days to Merck if it causes the subject to be excluded from the trial, or is the result of a protocol-specified intervention, including but not limited to washout or discontinuation of usual therapy, diet, placebo treatment or a procedure.

For the time period beginning at treatment allocation through 30 days following cessation of treatment, any ECI, or follow up to an ECI, whether or not related to Merck's product, must be reported within 2 working days to Merck, either by electronic media or paper.

Events of clinical interest for this trial include:

1. an overdose of Merck's product, as defined in Section 7.2.2 - Definition of an Overdose, that is not associated with clinical symptoms or abnormal laboratory results.
3. 2. In addition to overdose, Hepatic ECIs will include any of the following events. All of these events will require holding pembrolizumab, notification of Merck within 24 hours (as an AE), and, if appropriate, hepatology consultation. All cases of permanent discontinuation must also be reported within 7 days. For dose interval modification and treatment guidelines for these events, refer to Section 5.2.1.

### a. ALT:

# Proprietary Information of MD Anderson

Protocol # 2016-0251

Date: February 24, 2020

109

- i. Among subjects with Day 1 ALT  $<2 \times$  ULN, ALT  $\geq 5 \times$  ULN
- ii. Among subjects with Day 1 ALT  $\geq 2 \times$  ULN, ALT  $>3 \times$  the Day 1 level
- iii. ALT  $>500$  U/mL regardless of baseline level

*(Subjects with ALT  $>5 \times$  ULN at Day 1 are not eligible for enrollment)*

**b. AST:**

- i. Among subjects with Day 1 AST  $<2 \times$  ULN, AST  $\geq 5 \times$  ULN
- ii. Among subjects with Day 1 AST  $\geq 2 \times$  ULN, AST  $>3 \times$  the Day 1 level
- iii. AST  $>500$  U/mL regardless of baseline level

*(Subjects with ALT  $>5 \times$  ULN at Day 1 are not eligible for enrollment)*

**c. Total Bilirubin:**

- i. Among subjects with Day 1 levels  $<1.5$  mg/dL, a value of  $>2.0$  mg/dL
- ii. Among subjects with Day 1 levels that are  $\geq 1.5$  mg/dL, a value  $\geq 2 \times$  the D1 level
- iii. Total bilirubin  $>3.0$  mg/dL regardless of baseline level

*(Subjects with Total Bilirubin  $>2.0$  mg/dL at Day 1 are not eligible for enrollment)*

**d. Regardless of laboratory values, hepatic decompensation diagnosed clinically, including:**

- i. New onset ascites
- ii. GI bleeding suggestive of portal hypertension (eg esophageal or gastric varices)
- iii. Encephalopathy

*(Subjects with clinically apparent ascites or encephalopathy, or untreated varices are not eligible for enrollment)*

4. Reactivation of HBV and HCV for those with underlying infection.

### 7.2.4.3 Protocol-Specific Exceptions to Serious Adverse Event Reporting

Efficacy endpoints as outlined in this section will not be reported to Merck as described in Section 7.2.1. Specifically, the suspected/actual events covered in this exception include any event that is disease progression of the cancer under study.

The investigator will monitor unblinded aggregated efficacy endpoint events and safety data to ensure the safety of the subjects in the trial. Any suspected endpoint which upon review is not progression of the cancer under study will be forwarded to the IND office and Merck Global Safety as an SAE within 24 hours of determination that the event is not progression of the cancer under study.

# Proprietary Information of MD Anderson

Protocol # 2016-0251

Date: February 24, 2020

110

## 7.2.5 Evaluating Adverse Events

An investigator who is a qualified physician will evaluate all AEs according to the NCI CTCAE, version 4.0. Any AE which changes NCI CTCAE grade over the course of a given episode will have each change of grade recorded on the AE CRF.

All AEs regardless of NCI CTCAE grade must also be evaluated for seriousness.

## 7.2.6 Responsibility for Reporting Adverse Events

All AEs will be reported to regulatory authorities, IRB/ERCs and investigators in accordance with all applicable global laws and regulations. regulations, i.e., per International Council for Harmonisation (ICH) Topic E6 (R1) Guidelines for GCP.

# 8.0 STATISTICAL ANALYSIS PLAN

This section outlines the statistical analysis strategy and procedures for the study. If, after the study has begun, but prior to any final database lock, changes made to primary and/or key secondary hypotheses, or the statistical methods related to those hypotheses, then the protocol will be amended (consistent with ICH Guideline E-9). Changes to exploratory or other non- confirmatory analyses made after the protocol has been finalized, but prior to final database lock, will be documented as a protocol amendment. There will be a separate biomarker plan. HCV end points will be combined and described in Section 8.13.

## 8.1 Statistical Analysis Plan Summary

Key elements of the statistical analysis plan are summarized in Table 15. The comprehensive plan is provided in Sections 8.2 to 8.13.

Table 15 Key Elements of the Statistical Analysis Plan

Study Design Overview	A Phase II Study of Pembrolizumab (MK-3475) in Hepatitis C Virus Positive and Negative Subjects with Advanced Hepatocellular Carcinoma Who Progressed on or Were Intolerant to First-Line Systemic Therapy
Treatment Assignment	This is a single arm open-label study.
Analysis Populations	Efficacy: All Subjects as Treated (ASaT) Safety: ASaT
Primary Endpoints	Correlative Biomarkers, Safety and Tolerability.
Statistical Methods for Key Efficacy Analyses	Objective Response Rate (ORR) based on RECIST 1.1 assessed by the MDACC imaging staff. The estimate of the ORR, along with its 90% confidence interval (CI) based on the Clopper-Pearson method (48), will be provided.
Statistical Methods for Key Safety Analyses	Counts and percentages of subjects with AEs will be provided.

# Proprietary Information of MD Anderson

Protocol # 2016-0251

Date: February 24, 2020

111

Interim Analysis	No planned interim analysis for this Phase II study.
Multiplicity	No multiplicity adjustment is planned in this Phase II study.
Sample Size and Power	The planned sample size is 15 subjects per Arm

## 8.2 Responsibility for Analyses

The statistical analysis of the data obtained from this study will be the responsibility of the Clinical Biostatistics department of Merck.

This trial is being conducted as a non-randomized, open-label study, i.e., subjects, investigators, and Merck personnel will be aware of subject treatment assignments after each subject is enrolled and treatment is assigned.

The Clinical Biostatistics department will generate the allocation schedule(s).

## 8.3 Hypotheses/Estimation

Objectives and hypotheses of the study are stated in Section 3.

## 8.4 Analysis Endpoints

Efficacy and safety endpoints that will be evaluated are listed below.

### 8.4.1 Exploratory Efficacy Endpoints

#### 8.4.1.1 Primary Endpoints

The primary endpoints are safety and tolerability of pembrolizumab (Section 4.2.4.1) and SVR12 (Section 4.2.4.1).

#### 8.4.1.2 Secondary Exploratory/Efficacy Endpoints

- ORR is defined as the proportion of the subjects in the analysis population who have a CR or PR. Responses are based on assessments by the blinded M.D. Anderson radiology per RECIST 1.1
- DOR is defined as the time from first response to disease progression in subjects who achieve a PR or better, based on assessments by the blinded M.D. Anderson radiology per RECIST 1.1.
- DCR is defined as the percentage of subjects who have achieved confirmed CR or PR or have demonstrated SD for at least 24 weeks prior to any evidence of progression, based on assessments by the blinded M.D. Anderson radiology per RECIST 1.1
- TTP is defined as the time from randomization to the first documented disease progression. If there is no documented disease progression, TTP is censored at last

# Proprietary Information of MD Anderson

Protocol # 2016-0251

Date: February 24, 2020

112

tumor assessment date. It will be assessed by the blinded M.D. Anderson radiology per RECIST 1.1.

- PFS is defined as the time from allocation to the first documented disease progression per RECIST 1.1 based on assessments by the blinded M.D. Anderson radiology or death due to any cause, whichever occurs first.
- OS is defined as the time from first dose of study medication to death due to any cause.

## 8.4.1.3 Exploratory Efficacy Endpoints

The exploratory endpoints listed in Section 3.0 (i.e., ORR, DOR, DCR, TTP, PFS, and OS per iRECIST), are defined in the same way as their counterpart in Section 8.4.1.2, except that their disease progression will be assessed, and then confirmed (4 weeks later), by M.D. Anderson radiology per iRECIST, instead of per RECIST 1.1.

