# Proprietary Information of MD Anderson

Protocol # 2016-0251

Date: February 24, 2020

33

documented PD according to RECIST 1.1 and with confirmatory assessment as required per iRECIST, or death due to any cause, whichever occurs first. If a subject does not have a documented date of progression or death, PFS will be censored at the date of the last adequate assessment.

- 4) OS, defined as the time from the date of the first dose of study to the date of death due to any cause. Censoring will be performed using the date of last known contact for those who are alive at the time of analysis.
- 5) Viral resistance measurements will be made on any subject who had detectable virus above 1000 IU/mL after completing Zepatier therapy. Blood samples for viral resistance assays and the determination of the sequence of RAVs will be obtained.

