# Proprietary Information of MD Anderson

Protocol # 2016-0251

Date: February 24, 2020

34

a subject is clinically stable, additional imaging may be performed to confirm radiographic progression. iRECIST will be used by Investigators to assess tumor response and progression and make treatment decisions as well as for exploratory efficacy analyses where specified.

iRECIST will be used by M.D. Anderson Cancer Center (MDACC) investigators to assess tumor response and progression, and make treatment decisions as well as by M.D. Anderson Department of Diagnostic Imaging in support of all secondary and exploratory response endpoints. Confirmation of PD for iRECIST endpoints will be taken from central imaging (this will be done by Quantitative Imaging Analysis Core [QIAC] at MDACC) retrospectively, according to iRECIST definition.

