## 7.1.4.1.3 End of Treatment and Follow-up Tumor Imaging

In subjects who discontinue trial treatment, tumor imaging should be performed at the time of treatment discontinuation ( $\pm$ 4 week window). If a previous scan was obtained within 4 weeks prior to the date of discontinuation, then a scan at treatment discontinuation is not mandatory. In subjects who discontinue trial treatment due to documented disease progression, this is the final required tumor imaging.

In subjects who discontinue trial treatment without documented disease progression, every effort should be made to continue monitoring their disease status by tumor imaging using the same imaging schedule used while on treatment (every 63 days  $\pm$ 7 days) to monitor disease status until the start of a new anticancer treatment, disease progression, pregnancy, death, or the end of the trial, whichever occurs first.

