## 7.1.4.1.5 iRECIST Assessment of Disease

iRECIST is based on RECIST 1.1, but adapted to account for the unique tumor response seen with immunotherapeutic drugs. iRECIST will be used by the Investigator to assess tumor response and progression, and make treatment decisions. When clinically stable, subjects should not be discontinued until progression is confirmed by the Investigator, working with local radiology, according to the rules outlined in Section 12.2. This allowance to continue treatment despite initial radiologic PD takes into account the observation that some subjects can have a transient tumor flare in the first few months after the start of immunotherapy, and then experience subsequent disease response. This data will be captured in the clinical database.

Clinical stability is defined as the following:

- Absence of symptoms and signs indicating clinically significant progression of disease
- No decline in ECOG performance status
- No requirements for intensified management, including increased analgesia, radiation, or other palliative care

Any subject deemed **clinically unstable** should be discontinued from study treatment at site-assessed first radiologic evidence of PD, and is not required to have repeat tumor imaging for confirmation of PD by iRECIST.

If the Investigator decides to continue treatment, the subjects may continue to receive study treatment and the tumor assessment should be repeated 4 to 8 weeks later to confirm PD by iRECIST, per Investigator assessment.

If repeat imaging does not confirm PD per iRECIST, as assessed by the Investigator, and the subject continues to be clinically stable, study treatment may continue and follow the regular imaging schedule. If PD is confirmed, subjects will be discontinued from study treatment.

If a subject has confirmed radiographic progression (iCPD) as defined in **Section 12.2**, study treatment should be discontinued; however, if the subject is achieving a clinically meaningful benefit, an exception to continue study treatment may be considered following consultation with Merck. In this case, if study treatment is continued, tumor imaging should continue to be

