## Proprietary Information of MD Anderson

Protocol # 2016-0251

Date: February 24, 2020

94

performed following the intervals as outlined in Section 6 and submitted to the central imaging vendor.

A description of the adaptations and iRECIST process is provided in Section 12.2, with additional details in the iRECIST publication [Seymour et al, 2017]. A summary of imaging and treatment requirements after first radiologic evidence of progression is provided in Table 11 and illustrated as a flowchart in Figure 2.

Table 11 Imaging and Treatment After First Radiologic Evidence of Progressive Disease

	Clinically Stable		Clinically Unstable	
	Imaging	Treatment	Imaging	Treatment
First radiologic evidence of PD by RECIST 1.1	Repeat imaging at 4 to 8 weeks to confirm PD.	May continue study treatment at the Investigator's discretion while awaiting confirmatory tumor imaging by site by iRECIST.	Repeat imaging at 4 to 8 weeks to confirm PD per Investigator's discretion only.	Discontinue treatment
Repeat tumor imaging confirms PD (iCPD) by iRECIST per Investigator assessment	No additional imaging required.	Discontinue treatment (exception is possible upon consultation with Merck).	No additional imaging required.	Not applicable
Repeat tumor imaging shows iUPD by iRECIST per Investigator assessment	Repeat imaging at 4 to 8 weeks to confirm PD. May occur at next regularly scheduled imaging visit.	Continue study treatment at the Investigator's discretion.	Repeat imaging at 4 to 8 weeks to confirm PD per Investigator's discretion only.	Discontinue treatment
Repeat tumor imaging shows iSD, iPR, or iCR by iRECIST per Investigator assessment.	Continue regularly scheduled imaging assessments.	Continue study treatment at the Investigator's discretion.	Continue regularly scheduled imaging assessments.	May restart study treatment if condition has improved and/or clinically stable per Investigator's discretion. Next tumor imaging should occur according to the regular imaging schedule.

Abbreviations: iCPD=iRECIST confirmed progressive disease; iCR=iRECIST complete response; iRECIST=modified Response Evaluation Criteria in Solid Tumors 1.1 for immune-based therapeutics; iSD=iRECIST stable disease; iUPD=iRECIST unconfirmed progressive disease; PD=progressive disease; RECIST 1.1=Response Evaluation Criteria in Solid Tumors 1.1.

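### iRECIST progression needs a confirmatory scan that clinically unstable subjects are not required to have, so iRECIST TTP is censored at the progression scan and biased upward; PFS is biased less

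*Combined protocol and SAP*

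**What the plan says.** Section 8.4.1.3 takes the iRECIST endpoints from 8.4.1.2 with one change: "their disease progression will be assessed, and then confirmed (4 weeks later), by M.D. Anderson radiology per iRECIST". Section 4.3.4.4 adds that "Confirmation of PD for iRECIST endpoints will be taken from central imaging", read retrospectively, so a second scan must exist.

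Under 7.1.4.1.5, repeated in 12.2, a clinically unstable subject leaves treatment at the first radiologic progression seen by the site and "is not required to have repeat tumor imaging for confirmation of PD by iRECIST". Table 11 makes the repeat optional for these subjects: "Repeat imaging at 4 to 8 weeks to confirm PD per Investigator's discretion only". Section 7.1.4.1.3 says of the discontinuation scan: "In subjects who discontinue trial treatment due to documented disease progression, this is the final required tumor imaging".

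On censoring, 8.4.1.2 says of TTP: "If there is no documented disease progression, TTP is censored at last" tumor assessment. PFS in the same section also counts death, "or death due to any cause, whichever occurs first". Section 4.3.4.2 applies censoring only when neither progression nor death is documented; then "PFS will be censored at the date of the last adequate assessment".

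Table 17 has no row for an unconfirmed iRECIST progression (iUPD). Table 18, which censors deaths after missed assessments, covers DOR only. Section 12.2 requires confirmation before iCPD and says nothing about an iUPD that is never re-imaged.

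**The concern.** The endpoint rule needs a second scan; the conduct rules do not require one for the subjects doing worst. Instability in 7.1.4.1.5 means signs of clinically significant progression, a fall in ECOG status, or a need for intensified management. Whether a progression becomes an event therefore depends on prognosis, whereas the planned Kaplan-Meier analysis assumes that censoring carries no such information.

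At stake is how the iRECIST estimates are read. Section 4.3.4.4 argues that RECIST 1.1 may underestimate pembrolizumab's benefit in about 15% of subjects. An iRECIST TTP lengthened only by this censoring would look like the expected finding.

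**Working it through.** **Plan's figures.** The documents give no median, event count or share never re-imaged for iRECIST TTP or PFS, so there is no figure to reproduce. The check traces the rules and then illustrates the size.

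**Tracing one subject.** An unstable subject has first progression at a scheduled scan, stops treatment and is not scanned again.
- RECIST 1.1 TTP (8.4.1.2): event at that scan.
- iRECIST TTP (8.4.1.3): the progression is unconfirmed, so none is documented on this scale. The subject is censored at the last assessment, which is that scan. Death is not a TTP event.
- iRECIST PFS: event at death if death precedes cut-off; otherwise censored at that scan. Section 2.1 follows survival every 12 weeks, so most deaths should be captured.

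**Size for TTP, continuous time.** Assume exponential TTP with hazard λ and a fraction f of first progressions never re-imaged. Events then occur at hazard (1−f)λ, so the estimated median is ln 2 / [(1−f)λ], which is 1/(1−f) times the true one.
- f = 20%: 1/0.8 = 1.25.
- f = 40%: 1/0.6 = 1.67.

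**Size for TTP, 9-week scans.** Nine weeks is 9 × 12/52.18 = 2.07 months, so two scans fall before 6 months. With median m, the chance of progression in one interval is p = 1 − exp(−ln 2 × 2.07/m). If every first progression counts, the 6-month estimate is (1−p)². Under the literal rule it is [1 − (1−f)p]².

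| m (assumed) | p | f (assumed) | All counted | Literal rule | Difference |
|---|---|---|---|---|---|
| 3 months | 0.380 | 20% | 38.4% | 48.4% | 10.0 points |
| 3 months | 0.380 | 40% | 38.4% | 59.6% | 21.2 points |
| 4.5 months | 0.273 | 20% | 52.9% | 61.1% | 8.2 points |
| 4.5 months | 0.273 | 40% | 52.9% | 69.9% | 17.1 points |

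A Kaplan-Meier simulation with 100,000 subjects per scenario gives the same values to within a point. On this grid the median moves in whole scan intervals: unchanged at f = 20%, one scan later at f = 40% (4.14 to 6.21 months, and 6.21 to 8.28).

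**Size for PFS.** The same simulation adds these assumptions: median survival of 2 or 4 months after the scan in subjects never re-imaged, death without progression at a median of 30 months, and cut-off 6 to 21 months after entry. Of the never re-imaged progressors, 70% to 88% die before cut-off and so become PFS events. Six-month PFS:
- m = 3: 33% with all counted; 37–40% (f = 20%) or 41–46% (f = 40%) under the literal rule.
- m = 4.5: 46% with all counted; 49–51% or 52–55% under the literal rule.

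The upward shift is about 3 to 12 points, against 8 to 21 for TTP.

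**The case against.** Several stronger readings are tempting, and the documents do not support them.

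- *PFS is censored at the progression scan too.* Not generally. Death is a PFS event, survival is followed every 12 weeks, and the rule discarding deaths after missed assessments belongs to DOR. Unstable progressors are likely to die early, so most of their PFS events come late but are not lost.
- *Confirmation is impossible for unstable subjects.* It is optional. Table 11 allows a repeat scan and has a row for unstable subjects whose repeat shows stable disease or response. Section 7.1.4.1 also has unscheduled images that show progression read by M.D. Anderson radiology. Only subjects never re-imaged are affected.
- *About 5 of 15 subjects per arm are affected.* Section 4.3.1 reports 34 of 104 with progressive disease in the cited pembrolizumab trial, and 34/104 × 15 = 4.9. That count makes no distinction between stable and unstable or re-imaged and not, so it does not estimate those affected.
- *A confirming scan at week 6 fails the rule.* That reads a parenthesis as an exact day. Section 5.6.2 (treatment after initial progression) says at least 4 weeks, and 7.1.4.1.2, 7.1.4.1.5, Table 11 and 12.2 say 4 to 8 weeks. The wordings need reconciling.

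It can also fairly be said that the plan never states the censoring outright: it follows by default from silence. Whether the iRECIST publication that the protocol cites fills the gap cannot be settled from these documents. The objective in 4.1 is only to estimate the iRECIST endpoints, with about 15 subjects per arm and no test. All this limits the importance of the point. It does not remove the gap, because an analyst following 8.4.1.2 and 8.4.1.3 as written has no other instruction.

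**Conclusion.** The point stands for iRECIST TTP and, in weaker form, for iRECIST PFS. An unstable progressor who is never re-imaged is censored for TTP at the scan that showed progression. This biases TTP upward, by a factor of 1/(1−f) in the median under exponential TTP. That formula applies to TTP only. For PFS the bias has the same direction but is smaller, since the event usually moves to the date of death. Every value of f, m and post-progression survival used here is an assumption.

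The endpoints are exploratory and the primary endpoints are untouched. A reader might infer that secondary PFS is also affected, because 4.3.4.2 mentions confirmation per iRECIST in defining it. Section 8.4.1.2 defines RECIST 1.1 TTP and PFS without confirmation, so the documents do not establish this; the two sections should be reconciled.

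**What to change.** Add to 8.4.1.3:

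- (a) A confirmed iUPD is an event dated at the first iUPD.
- (b) An iUPD with no later evaluable scan because of clinical instability, stopping for progression, new anticancer therapy or death is an event dated at that iUPD.
- (c) A persistent iUPD that has not resolved by the last available scan is an event dated at the first iUPD.
- (d) An iUPD that resolves to iSD, iPR or iCR is not an event.
- (e) An iUPD whose confirmatory scan is still pending at data cut-off, in a subject still under imaging follow-up, is censored at the iUPD scan and counted separately.
- (f) The confirmation window for analysis is aligned with the 4 to 8 weeks under which the scans are collected.
- (g) The number of unconfirmed iUPDs is reported per arm, with a sensitivity analysis that censors them.

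The change is to analysis wording only, with no extra imaging and no change in patient management. The iRECIST TTP and PFS estimates become slightly less favourable. Rule (b) will also count an occasional pseudo-progression that was never re-imaged; the sensitivity analysis in (g) shows how much that could matter.
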